Hypothesis 2 (H2): Relative to those treated at UC clinics, eligible 18-75 year-old prediabetes patients with uncontrolled CV risk factors at CDS clinics will have significantly more favorable trajectories in specific CV risk factors, including BP, lipids, smoking, HbA1c, and weight over a median 24-month follow up.

Hypothesis 3 (H3): Relative to those treated at UC clinics, eligible 18 to 75 year-old prediabetes patients at high CV risk treated at CDS clinics will have significantly more favorable patterns of metformin and statinuse over a median 24-month follow up.

Specific Aim 2. Assess the cost of the CDS intervention from the health system (payer) perspective through utilization analyses.

[figure not shown]
Hypothesis 4 (H4): After controlling for demographics and baseline clinical status, eligible patients with prediabetes treated in UC clinics versus CDS clinics will have significantly lower annual healthcare costs from the index date over a median follow up of 24 months.

Specific Aim 3: Describe critical facilitators and barriers for the prediabetes CDS implementation process, outcomes, and future dissemination using a mixed-methods approach.

Note that a previously included cost-effectiveness hypothesis (Hypothesis 5) was not tested due to lack of efficacy of the study intervention. Project results will provide a template for implementation of personalized CDS tools in rural and urban health settings, resulting in more efficient, effective rural healthcare that can be applied across many clinical domains, incorporates patient treatment preferences, and could substantially and sustainably improve the quality of CV care and clinical outcomes of millions of Americans with prediabetes in medically underserved areas.

Overview of Study Implementation Process and Design: The implementation process has four primary components (Figure 1): a) initial organizational engagement; b) adapting and piloting the Prediabetes CDS with Essentia primary care providers and patients; c) a group-randomized controlled study of the adapted CDSin 34 primary care clinics blocked on size and Essentia geographic service area; and d) evaluation of the implementation process and outcomes. It is critical to note that implementation is an iterative process, both in the adaptation

phase and during the randomized controlled trial of implementation and outcomes. Continuous feedback is provided to and

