Step F: Iterative Use of the Prediabetes CDS over a Series of Visits. A key design feature of this intervention is its repeated use at all office visits of eligible patients during the intervention period. The CDS is automatically activated at any visit during the study period for eligible patients and provides updated treatment priorities and recommendations at each visit. Pilot data indicate that eligible patients average 4-6 primary care visits during a 24 month period, assuring that nearly all intervention patients have at least 3 exposures to the CDS. The CDS can also be manually activated by the PCP. In our previous study, almost 70% of eligible PCPs maintained use of the CDS system. With strong support from Essentia leaders and PCP leaders, we expect similar use rates.

Prediabetes patients converting to diabetes will continue to receive appropriate CV risk reduction prioritization and evidence-based glucose and aspirin treatment recommendations, thus facilitating timely treatment transition for newly diagnosed diabetes and reducing the lag time often reported between conversion to diabetes and being clinically diagnosed and treated.

Implementation of the Prediabetes CDS Intervention: Key implementation stages include: organizational engagement; adapting, piloting, and refining the Prediabetes CDS; and implementing the Prediabetes CDS group-randomized study. Key informant interviews, focus groups, surveys, usability testing, EMR data, and continuous quantitative and qualitative feedback between researchers and stakeholders will be used to monitor the implementation process and outcomes.

Organizational Engagement: As part of the initial engagement process, Essentia leaders and PCP leaders have already provided letters of support for the prediabetes CDS. Further engagement with Essentia leadership, informatics personnel, and key providers will occur through in-person meetings, conference calls, informational meetings, and identification of critical personnel to participate in the development, adaptation, and piloting processes of this study.

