Aim #1- (a) Cardiovascular Risk Trajectories (H1): There is no validated CV risk engine developed with a prediabetes population. Therefore, we propose to use the ACC/AHA 10-year pooled CV risk engine to estimate annual rate of change in CV risk as our primary outcome. We will use the lipid equation for patients with lipid data available to calculate CV risk at the index and all post-index visits and, to minimize missing CV risk values, the BMI equation at the index and all post-index visits for the remaining patients. The BMI equation estimates higher CV risk relative to the lipid equation. Because the calculation method will be consistent across all visits within each patient this difference will not bias the estimated rate of change in CV risk. CV risk scores for each patient will be calculated at each primary care visit from the index through the entire follow-up period using available EHR data elements. As depicted in Figure 2 Step A, at each visit we will search for the most recent data elements, looking back over a period appropriate for each risk component (i.e., 12 months for BP values or medications, DM diagnosis, smoking, BMI; 48 months for lipids). H1 will be supported if the annual rate of change in CV risk scores from the index visit through the end of the follow-up period is lower (ie, less increase) among patients in the CDS relative to UC clinics; (b) Modifiable diabetes and CV risk factors (H2): Risk factors needed to calculate the CV risk scores (weight, systolic blood pressure, HDL-c, LDL-c, totalcholesterol, smoking), are extracted from EHR files as in Figure 2 Step A. H2 will be supported if annual rate of change in CV risk component trajectories are lower among patients in the CDS relative to UC clinics; (c) Metformin and statin use (H3): Data to assess drug treatment are from EHR files such as prescribed medications. The presence or absence of appropriate drug use will be assessed at each visit. H3 will be supported if appropriate drug use improves over the follow-up period among patients in the CDS clinics relative to UC patients.

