Measures of Covariates for Primary and Secondary Analyses: One predictor of CV risk, risk factor, and drug use outcomes is the binary indicator for study condition (CDS or UC). The second key predictor is time elapsed in years between the patient's index visit to each subsequent measurement. Several other measures merit consideration as dependent outcomes, moderators or mediators in primary analyses. These include (a) number of PCP patient encounters, (b) patient characteristics including demographics and pre-intervention clinical values and comorbidities (EHR ICD-10 diagnosis codes and problem lists), and (c) provider characteristics such as age, gender, type of provider, full-time or part-time work status,, specialty board certification status, and proportion of eligible study patients. Patient or provider characteristics may also be used to adjust for covariate imbalance introduced by clinic randomization.

Analysis Plan.

Aim 1 Analytic Approach. Aim 1 pertains to the effectiveness of the Prediabetes CDS intervention, predicting that it will improve the annual rate of change in CV risk (CVR) and individual risk factors relative to UC. Patients age 40-75 at index are included in the Aim 1 analyses because the CDS was programmed to deliver the intervention via treatment recommendations (Figure 2, Step B) to this age group. Rate of change outcomes (e.g., H1, H2) will be tested using random coefficients models in which all available index and post-index outcomes (H1 CV risk, H2 CV risk factors) will be predictedfrom fixed effects for clinic-randomized treatment group, years elapsed since index CVR, the treatment by years elapsed interaction and the index outcome value. Outcomes measured only once per person will follow the same approach, omitting predictors that incorporate years elapsed since index and where warranted including an offset for follow-up time.

Random clinic and patient intercepts will account for clustered observations as appropriate. The link function and error distribution for each model will be determined by the distribution of each outcome. The relationships between years elapsed and CV risk and risk factor outcomes are expected to be linear. The tenability of this assumption will be checked for each outcome and more complex relationships (e.g., non-linear, spline) modeled if warranted.

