The years elapsed parameter will estimate the annual rate of change in CV risk and risk factors among patients in UC clinics in the absence of intervention, while the treatment by years elapsed parameter estimates the difference in the annual rate of change among patients in the CDS relative to UC clinics. It is expected that CV risk will decrease, or increase at a slower rate, among patients in CDS relative to UC clinics. Similar patterns of improvement, or slower worsening, are expected for CV risk factors. Finally, the treatment group parameter is expected to estimate more appropriate pharmacologic use among patients in CDS compared to UC clinics.

2.2.6.1 H1 Sample size justification. We conducted a power analysis to estimate theminimum detectable slope of the treatment by time parameter (power=.80, α_2 =.05) given the anticipated sample size (15 CDS clinics, 7-11 providers per clinic * 25 patients per provider = 2625-4125 CDS patients, 3 CVR per patient).. The patient sample size was divided by the design effect, Neff = N / [1 + (n_{clus} – 1) ρ], to approximate the effective independent patient sample size (Neff) implied by clinic intraclass correlations (ICC) of ρ = .001-.02. The CVR sample sizes (Neff patient * 3 CVR/pt) were divided by the design effect implied by a patient ICC=0.80. The resulting effective CVR sample sizes were used to estimate the minimum detectable standardized linear regression coefficient (β_{CDS}) relative to β_{UC} =0. When ICC_{clin}=0.001, the minimum detectable β_{CDS} =0.044-0.055; when ICC_{clin}=0.005 β_{CDS} =0.061-0.070; and when ICC_{clin}=0.02 β_{CDS} =0.103-0.108.

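### The plan does not fix which model and coefficient decide H3 (metformin and statin use); if the H1/H2 model is used, the parameter it names is the arm difference at the index visit

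*Combined protocol and SAP*

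**What the plan says.** Four places in the combined protocol and SAP bear on H3.

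- **Hypothesis 3** predicts "significantly more favorable patterns of metformin and statinuse over a median 24-month follow up". It names neither a level nor a slope.
- **Definition and Measurement of Variables, Aim #1 (c)** sets the measurement and the decision rule: "The presence or absence of appropriate drug use will be assessed at each visit", and "H3 will be supported if appropriate drug use improves over the follow-up period among patients in the CDS clinics relative to UC patients".
- **Measures of Covariates** names study condition as a predictor of drug use as well as of CV risk and risk factors. The next sentence names elapsed time as the second key predictor.
- **Aim 1 Analytic Approach** gives the repeated-measures model: "Rate of change outcomes (e.g., H1, H2) will be tested using random coefficients models in which all available index and post-index outcomes" are predicted from treatment group, years since index, "the treatment by years elapsed interaction and the index outcome value". A second clause reads: "Outcomes measured only once per person will follow the same approach, omitting predictors that incorporate years elapsed since index". The section then interprets the coefficients. Years elapsed is the UC rate of change, treatment by years is the difference in rates for CV risk and risk factors, and for drug use "the treatment group parameter is expected to estimate more appropriate pharmacologic use among patients in CDS compared to UC clinics".

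**The concern.** The decision rule concerns drug use followed visit by visit and improving over time. The coefficient named for it is the treatment group parameter, and what that measures depends on a model choice that the plan leaves open.

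If treatment-by-years is kept, the parameter is the arm difference at years = 0. If it is dropped and only post-index visits are analysed, the parameter is an average difference over follow-up. The first cannot show a gradual gain; the second can.

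A gradual gain is a plausible course here. Step F says: "A key design feature of this intervention is its repeated use at all office visits of eligible patients during the intervention period". If prescribing builds up over repeated exposures, the H3 conclusion could turn on which model the analyst fits.

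**Working it through.** **1. What the named parameter estimates in the H1/H2 model.** Write the model on a linear scale, for patient i at time t, as

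E[Y(t)] = b0 + b1·Trt + b2·t + b3·Trt·t + b4·Y(0).

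The fitted arm difference at time t is b1 + b3·t, so b1 is the difference at t = 0. The index rows are among the outcomes, and the index value is also a covariate. At t = 0 the outcome therefore equals its own covariate, and the true adjusted arm difference D(0) is zero whatever happens later. The estimate of b1 leaves zero only where a straight line fails to follow the true course.

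**2. Exact values.** With the same visit times in both arms, least squares gives

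b3 = Σ(t − t̄)(D − D̄) / Σ(t − t̄)², b1 = D̄ − b3·t̄.

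Inputs: three records per patient come from the H1 sample size section, and a median of six visits over 24 months from the Study Participants section. Equal spacing is my assumption.

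*Gain growing by d per year, D = d·t.* The line fits exactly, so b1 = 0 and b3 = d on any schedule.

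*Immediate gain of d from the first post-index visit, records at 0, 1, 2 years.* D = (0, d, d), D̄ = 2d/3, t̄ = 1, Σ(t − t̄)² = 2.
- b3 = (−1·0 + 0·d + 1·d)/2 = d/2
- b1 = 2d/3 − d/2 = d/6

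*The same gain, index plus six visits every four months.* D̄ = 6d/7, t̄ = 1, Σ(t − t̄)² = 28/9, Σ(t − t̄)D = d.
- b3 = 9d/28 = 0.32d
- b1 = 6d/7 − 9d/28 = 15d/28 = 0.54d

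As visits become very frequent, the index row loses weight and b1 for an immediate gain approaches d.

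*Contrast over post-index visits without time terms.* For the immediate gain it is d on either schedule. For the growing gain it is (d + 2d)/2 = 1.5d with three records, and d times the mean visit time, 7d/6, with seven. It picks up both courses.

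**3. Illustrative rejection rates.** From the H1 sample size section: 15 CDS clinics × 7 providers × 25 patients = 2,625 patients, three records, patient correlation 0.80, and clinic ICC 0.005 (inside the stated range .001–.02). Assumed: 15 UC clinics, 20% on the drug at index, a UC rise of 2 points per year, and a CDS gain of either 2 extra points per year (growth) or 4 points from the first post-index visit (step). Marginal logistic fits with clinic-robust standard errors, 1,000 data sets. Ranges are over three ways of generating the within-patient correlation.

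| Records | Course | Treatment group, interaction kept | Treatment-by-years | Post-index contrast, no time terms |
|---|---|---|---|---|
| 3 | growth | 8–23% | 98–99% | 97–99.7% |
| 3 | step | 67–99% | 93–98% | 99.9–100% |
| 7 | growth | 6–28% | 97–100% | 93–99% |
| 7 | step | 99–100% | 13–61% | 100% |

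With no effect and three records, rejection was 4.0–6.8%. It was not checked for seven records.

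**4. How firm these rates are.** Not very. With 3% on the drug at index (one generator, 400 data sets), the rates in the same order were:
- growth: 43/91/100% with three records, 46/87/100% with seven;
- step: 99.5/37/100% with three records, 100/22/100% with seven.

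Random-intercept logistic fits with three records gave 5.8–45.3% for the treatment group parameter under growth. Over all runs, including separately programmed ones, that figure ranged from about 3% to 46%, while the post-index contrast stayed at 93% or more. Random-intercept fits with seven records are not used, because their numerical accuracy was not established.

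**The case against.** The strongest defence is that the plan consistently treats H3 as a group contrast. The H1 and H2 rules speak of an annual rate of change and the H3 rule does not. The analytic section lists CV risk and risk factors as the rate outcomes and leaves drug use out. It gives slopes to those outcomes and the treatment group parameter to drug use. An index-adjusted contrast over follow-up would satisfy the H3 rule, and such a contrast performs well.

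Much of this stands. It is the likeliest intent, and the fix follows it. A reader might infer that the H3 rule demands the treatment-by-years test; the wording does not require that. It is also too strong to say that the plan gives H3 no model. Condition and time are named as predictors of drug use, link and random intercepts are set out for all outcomes, and the H1/H2 list is introduced as examples only.

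What the defence does not supply is a sentence removing the interaction. Elapsed time is named as a key predictor straight after drug use is mentioned. Time terms are dropped only for outcomes measured once per person, which H3 is not. And the H3 sentence closes a walk through the parameters of a model that contains the interaction.

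Two further inferences go too far. The plan does not prescribe the time-zero test for H3; that result is conditional on carrying over the H1/H2 model. Nor can a power figure be attached to H3, because the documents give no index use, effect size or power for it.

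**Conclusion.** The point holds as a gap in specification with a real consequence. H3's decision rule and its named coefficient agree only under a model that the plan does not state. Under the model that it does state for repeated outcomes, the named coefficient is zero for a gradual gain and only part of an immediate one (d/6 or 0.54d on the two schedules examined).

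The exact values rest on a linear scale, a common and evenly spaced visit schedule, and the index value used both as outcome and covariate. The rejection rates are illustrative only, because they depend on assumed index use, effect size and visit pattern. What survives every variation tried is that the H3 conclusion can depend on the coefficient read.

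The plan should be corrected, but the reach is limited. Aim #1 makes the rate of change in CV risk the primary outcome, and H1 and its power calculation are unaffected. The note on Hypothesis 5 shows that lack of efficacy was already known in this version. A reader might infer that the H3 test was chosen in light of results, but nothing in the documents shows that. The H2 rule's use of a lower rate for every component, HDL-c included, is a copy edit and no part of this finding.

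**What to change.** In the Aim 1 Analytic Approach, state that H3 is decided on the treatment parameter of a logistic mixed model of post-index, visit-level drug use, adjusted for drug use at index, with clinic and patient random effects and no treatment-by-years term. Reword the H3 rule under Aim #1 (c) to match: H3 is supported if appropriate use over the post-index visits, given index use, is higher in CDS than in UC clinics.

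Report treatment-by-years as a supporting analysis of the time course. It should not decide H3, because it is weak for an early step. Do not decide H3 on the treatment group parameter of any model that keeps treatment-by-years.

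The cost is a few sentences and no new data. There are three downsides. The averaged contrast does not itself show the time course. With strongly correlated visits, the quadrature of the mixed logistic fit should be checked. And the report must say which model was used, with any change made after H3 results were known labelled post hoc.

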from organizational leaders, providers, and patients to better understand the facilitators and barriers to implementation and to guide refinements of the CDS.

Group-Randomized Study Eligibility Criteria

Study Sites: The group-randomized controlled study will be implemented in 34 Essentia Health primary care clinics in Minnesota, North Dakota, and Wisconsin. Essentia clinics have used the Epic® EHR since 2004 and have, on average, 14 PCPs (range: 1-56) and 377 prediabetes patients at high CV risk per clinic. Eighty-four percent of the Essentia geographic service area is rural, with 56% of the patient population and 66% of clinics located in this rural area. Average household incomes are less than \$35,000 for 42% of patients, and 45% live in health professional shortage areas.

Study Participants: PCPs and Patients: To participate, PCPs must practice at one of the 34 Essentiaclinics and meet these eligibility criteria: (a) be an adult-care general internist, family physician, non-obstetric nurse practitioner, or physician assistant, and (b) provide ongoing primary care for 15 or more prediabetes adults ages 18-75 with high CV risk. There are currently 441 eligible PCPs which should ensure a more robust understanding of implementation barriers and facilitators in a large PCP community.

To be considered for inclusion in primary or secondary analyses, **patients** must meet all the following eligibility criteria at the time of their indexvisit: (a) be 18-75 years old, (b) have no evidence of diabetes in the previous 12 months (based on lab values, diagnosis codes, use of medications, or on problem list), (c) not be pregnant (d) have the most recent fasting plasma glucose of 100-125 mg/dL or HbA1c 5.7-6.4% within the prior 24 months, (e) have the most recent BMI $\geq 25 \text{ kg/m}^2$, (f) have at least one of the following uncontrolled CV risk factors: current smoking, a diagnosis

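### The H1 power paragraph assumes 15 equal-sized CDS clinics, but 34 clinics of very unequal size are randomised; the two departures partly cancel, and the detectable slopes should be restated for the actual design

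*Combined protocol and SAP*

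**What the plan says.** Section 2.2.6.1 (H1 Sample size justification) reports minimum detectable standardised slopes at "power=.80, α_2 =.05". The stated inputs are "15 CDS clinics, 7-11 providers per clinic * 25 patients per provider = 2625-4125 CDS patients, 3 CVR per patient". Clustering by clinic enters as one step: "The patient sample size was divided by the design effect", in the form Neff = N / [1 + (n_clus - 1)ρ], for "clinic intraclass correlations (ICC) of ρ = .001-.02". The repeated risk scores are then discounted by the "design effect implied by a patient ICC=0.80". The slopes given are 0.044-0.055, 0.061-0.070 and 0.103-0.108 at ICC 0.001, 0.005 and 0.02.

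The design is described differently elsewhere:

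- Overview of Study Implementation Process and Design: the controlled study is in "34 primary care clinics blocked on size and Essentia geographic service area". Specific Aim 1 also gives 34 clinics and two arms. No allocation ratio is stated.
- Study Sites: Essentia clinics have on average "14 PCPs (range: 1-56) and 377 prediabetes patients at high CV risk per clinic".
- Aim 1 Analytic Approach: the analysis is a mixed model with random clinic and patient intercepts.

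**The concern.** The design effect 1 + (n - 1)ρ is exact only when all clinics have the same size. A range of 1 to 56 PCPs rules that out for PCP counts, and blocking on size shows that the variation was known. Blocking balances the arms but does not remove the loss of information from unequal clinics. Separately, "15 CDS clinics, 7-11 providers per clinic" does not match half of 34, and no reason for 15 is given.

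This paragraph is the only power justification for the primary outcome. The protocol also records that the cost-effectiveness hypothesis was dropped for lack of efficacy, so the slopes the trial could have detected bear on what a null result can exclude.

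**Working it through.** **1. Reproducing the plan.** Inputs from section 2.2.6.1: 15 clinics; m = 7 × 25 = 175 or 11 × 25 = 275 patients per clinic; 3 scores per patient; patient ICC 0.80, so a repeated-measures design effect of 1 + 2(0.80) = 2.6; two-sided α 0.05 and power 0.80, so z-sum 1.96 + 0.84 = 2.80.

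Slope = 2.80 / √n, with n = {15m / [1 + (m - 1)ρ]} × 3 / 2.6.

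| ICC | Providers | Clinic design effect | n | Recomputed | Stated |
|---|---|---|---|---|---|
| 0.001 | 7 | 1.174 | 2,580 | 0.0552 | 0.055 |
| 0.001 | 11 | 1.274 | 3,736 | 0.0458 | 0.044 |
| 0.005 | 7 | 1.870 | 1,620 | 0.0696 | 0.070 |
| 0.005 | 11 | 2.370 | 2,008 | 0.0625 | 0.061 |
| 0.02 | 7 | 4.480 | 676 | 0.1077 | 0.108 |
| 0.02 | 11 | 6.480 | 735 | 0.1034 | 0.103 |

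Four of six figures reproduce, which confirms the equal-cluster formula and the 15 clinics. The lower ends 0.044 and 0.061 do not. With 12 providers per clinic (15 × 12 × 25 = 4,500 patients, not 4,125) the lower ends become 0.0443, 0.0614 and 0.1027, which match all three stated values.

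**2. Number of clinics.** 34 / 2 = 17 per arm if 1:1 (assumption). At fixed clinic size the slope scales by √(15/17) = 0.94, a fall of 6%.

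**3. How unequal are the clinics?** Take 34 clinics with mean 14, minimum 1 and maximum 56.

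- Smallest CV: the other 32 clinics are identical at (476 - 57)/32 = 13.09, giving CV 0.54.
- Largest CV: √[(14 - 1)(56 - 14)]/14 = 1.67.
- Range/4 as a rough SD: (55/4)/14 = 0.98.

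These are CVs of PCP counts. Using them for analysed patients assumes that patients are proportional to PCPs. I take 0.8-1.0 as a working range; it is an assumption.

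**4. Net effect, 17 clinics and unequal sizes.** Two methods:

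- (a) Simple design effect 1 + [(1 + CV²)m - 1]ρ, the direct extension of the plan's own formula.
- (b) Mixed-model relative efficiency 1 - CV²λ(1 - λ), with λ = mρ/(mρ + 1 - ρ), applied to the equal-cluster effective size.

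Changes are relative to the recomputed slopes in step 1, over 7-11 providers and CV 0.8-1.0. Power at those slopes is Φ(2.80/inflation - 1.96).

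| ICC | (a) net change | (a) power | (b) net change | (b) power |
|---|---|---|---|---|
| 0.001 | -2% to +4% | 77-81% | -2% to +3% | 78-82% |
| 0.005 | +7% to +18% | 66-74% | +2% to +8% | 73-78% |
| 0.02 | +15% to +28% | 59-68% | -2% to +3% | 78-82% |

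Worked example, ICC 0.02, 11 providers, CV 1.0, 17 clinics:

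- (a) The design effect is 1 + (2 × 275 - 1)(0.02) = 11.98, so n = (4,675/11.98) × 3/2.6 = 450 and the slope is 0.132, against 0.1034.
- (b) λ = 0.849, so efficiency is 1 - 0.849 × 0.151 = 0.872. Then n = (4,675/6.48) × 0.872 × 3/2.6 = 726 and the slope is 0.104.

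At the floor CV of 0.54, (a) gives a net -4% to +5%, and (b) gives slopes about 2% to 4% below the recomputed ones.

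**5. Reference distribution.** With 34 - 2 = 32 clinic df, (2.037 + 0.853)/2.802 = 1.032, so t quantiles add about 3%. Under (b) the overall net range at CV 0.8-1.0 becomes about +1% to +12%.

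All figures keep the plan's convention of using CDS-arm numbers against a usual-care slope fixed at 0.

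**The case against.** A reader might infer that power collapses at the largest ICC: with CV 0.8-1.0, the simple design effect and 15 clinics retained, the slopes rise by 22-36% at ICC 0.02 and power falls to 54-63%. The documents do not support that. It corrects for unequal size but not for the clinic count, and it ignores the planned analysis. With 17 clinics the same formula gives 59-68%, and the efficiency suited to a model with random clinic intercepts gives about 78-82%. Under that model the penalty is largest near ICC 0.005, not at 0.02.

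A reader might also infer that the reported range fixes the CV narrowly, for example at 0.66-1.2. That interval needs an assumed distribution such as gamma or lognormal; the mean and range alone give only 0.54-1.67. The range counts all PCPs, whereas the calculation uses 7-11 study providers. It is also stated for Essentia clinics generally, and the pilot section shows that some Essentia clinics lie outside the randomised study.

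In the plan's favour, the paragraph calls its effective sample size an approximation and spans a 20-fold range of ICCs. Using 15 clinics rather than 17 is conservative. No enrolment, estimand or test depends on the correction.

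These points limit the size of the concern. They do not explain the 15, supply the missing size term, or account for the two figures that do not follow from their inputs.

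**Conclusion.** The point holds as a mismatch between the power paragraph and the randomised design, with a modest and method-dependent effect on the slopes. At ICC 0.001 the stated slopes are roughly right under either method. At the larger ICCs the simple design effect gives a material understatement (net up to 18% at 0.005 and 28% at 0.02). The mixed model that the plan intends to fit gives at most about 8% before the t correction and 12% after it.

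This rests on three assumptions: 1:1 allocation, patients proportional to PCPs, and CV 0.8-1.0 among the 34 clinics. A CV nearer 0.54 would remove most of the net penalty; a CV well above 1 would enlarge it. Both methods carry the plan's own treatment of the slope as a clustered mean-type comparison. The failure of 0.044 and 0.061 to follow from 11 providers needs none of these assumptions. Nothing here shows that the trial enrolled too few patients or clinics.

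**What to change.** Rewrite section 2.2.6.1 so that it:

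- states the allocation ratio and the number of clinics per arm, and reconciles 15 CDS clinics with 34 randomised;
- reports the actual clinic sizes, or their CV, for analysed patients;
- restates the minimum detectable slopes with an unequal-cluster method matched to the planned mixed model, shows 1 + [(1 + CV²)n - 1]ρ as a conservative bound, and uses t quantiles on clinic df;
- replaces 0.044 and 0.061 by 0.046 and 0.0625 if 11 providers and 4,125 patients are correct, or corrects the provider and patient numbers if they are not.

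The cost is one paragraph and a short recalculation. Enrolment, data collection and the analysis model stay as they are. The downside is that some stated slopes become slightly less favourable.

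### The H1 minimum detectable slopes use the design effect for a mean and only one arm, so they do not describe the treatment-by-time term that will be tested

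*Combined protocol and SAP*

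**What the plan says.** Section 2.2.6.1 (H1 Sample size justification) sets out to find the smallest treatment-by-time slope that can be detected with "power=.80, α_2 =.05". The sample is "15 CDS clinics, 7-11 providers per clinic * 25 patients per provider = 2625-4125 CDS patients, 3 CVR per patient".

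The number of patients is first reduced by a clinic design effect, "Neff = N / [1 + (n_{clus} – 1) ρ"], "implied by clinic intraclass correlations (ICC) of ρ = .001-.02". The resulting patients, times 3 CVR values each, "were divided by the design effect implied by a patient ICC=0.80". What remains is treated as a number of independent observations and converted to a "minimum detectable standardized linear regression coefficient (β_{CDS}) relative to β_{UC} =0". The printed results are 0.044–0.055 at clinic ICC 0.001, 0.061–0.070 at 0.005 and 0.103–0.108 at 0.02.

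The Aim 1 Analytic Approach tests H1 on the interaction of treatment with years elapsed. It calls the analysis a random coefficients model, but the only random effects it names are intercepts: "Random clinic and patient intercepts will account for clustered observations as appropriate". No residual variance, slope variance or visit spacing is given.

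**The concern.** A design effect of 1 + (m − 1)ρ inflates the variance of a mean or of a between-patient contrast. Years elapsed varies within a patient. When each patient is followed over time, the patient's own level cancels from the slope, and a high within-patient correlation makes the slope more precise. The calculation therefore penalises the slope for a correlation that helps it.

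A second feature of the same paragraph works the other way. The tested term is a difference between two estimated slopes, but the calculation treats the UC slope as known to be zero.

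At stake is what the printed figures can be used for. The Specific Aims section reports that the cost-effectiveness hypothesis was dropped because the intervention had not shown efficacy. Readers will therefore ask what annual difference in CV risk the trial could have detected, and the only figures offered are standardised ones that do not match the tested term.

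**Working it through.** **Inputs from section 2.2.6.1:** 15 CDS clinics; 7 to 11 providers × 25 patients, so n_clus = 175 to 275 and N = 2625 to 4125; 3 CVR values per patient; patient ICC 0.80; clinic ICC 0.001, 0.005 and 0.02; power 0.80; α 0.05, read as two-sided, so z-sum = 1.960 + 0.842 = 2.802.

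**Assumed, because the documents do not give them:** visits at 0, 1 and 2 years; outcome variance 1; a UC arm equal in size to the CDS arm (15 clinics); patient slope SD (s_p) and clinic slope SD (s_c) in outcome SD per year.

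**1. Reproducing the plan.** MDE (minimum detectable effect) = 2.802 / √n, with n = {N / [1 + (n_clus − 1)·ICC]} × 3 / 2.6.

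| Clinic ICC | N = 2625: n, MDE (printed) | N = 4125: n, MDE (printed) |
|---|---|---|
| 0.001 | 2580, 0.0552 (0.055) | 3736, 0.0458 (0.044) |
| 0.005 | 1620, 0.0696 (0.070) | 2008, 0.0625 (0.061) |
| 0.02 | 676, 0.1077 (0.108) | 735, 0.1034 (0.103) |

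Four of six values match. Without the 2.6 divisor the N = 2625 column would be 0.034, 0.043 and 0.067, so the divisor was used. The two misses, including the lower end of "When ICC_{clin}=0.001, the minimum detectable β_{CDS} =0.044-0.055", match 12 providers per clinic (N = 4500: 0.0443, 0.0614, 0.1027) rather than the printed 11.

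**2. Patient-level factor.** Generalised least squares with three visits and exchangeable correlation 0.80 gives, relative to independent data, a variance factor of 2.6 for the mean. For the slope it gives 0.10 / 0.50 = 0.2. Taken alone, in one arm, the MDE is overstated by √(2.6/0.2) = 3.6.

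**3. Two arms.** Estimating the UC slope from an equal arm doubles the variance, so the one-arm MDE is too small by √2 = 1.41. Net of step 2: √(13/2) = 2.5.

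**4. Patient random slopes.** Per patient, the plan's slope variance is 2.6 / (3 × 2/3) = 1.3. The two-arm value is 2 × (0.2/2 + s_p²). The plan's clinic design effect is kept in both and cancels from the ratio.

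| s_p | Two-arm variance | Overstatement, √(1.3 / variance) |
|---|---|---|
| 0 | 0.20 | 2.5 |
| 0.1 | 0.22 | 2.4 |
| 0.2 | 0.28 | 2.2 |
| 0.3 | 0.38 | 1.8 |

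**5. Clinic slope variance.** Replace the plan's clinic design effect by an explicit term: variance of the slope difference = 2 × [(0.1 + s_p²)/N + s_c²/15]. Dividing the plan's standardised MDE by the SD of time, √(2/3) = 0.816, puts it in outcome SD per year: 0.0552 becomes 0.068.

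With N = 2625 and s_p = 0.2, the two-arm MDE is 0.029 at s_c = 0, 0.059 at s_c = 0.05 and 0.106 at s_c = 0.10. The break-even is s_c = √{15 × [(0.0676/2.802)²/2 − 0.14/2625]} = √(15 × 0.000238) = 0.060.

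Over N = 2625 to 4125 and s_p = 0 to 0.3, break-even lies at about 0.05–0.06 for ICC 0.001, 0.07–0.08 for 0.005 and 0.12–0.13 for 0.02. Below these values the printed MDE is too large, and above them it is too small. They are thresholds, not estimates.

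**The case against.** The strongest reply is that this changes little. The patient-level error on its own makes the printed values too large. The calculation takes the anticipated sample as given, so it did not set the number of clinics or patients. The document is dated March 2021 and already reports a lack of efficacy. With outcomes in hand, the confidence interval for treatment by years elapsed, which carries the observed variance, says what a null H1 excludes. All of that stands, and it limits the consequence. It does not make the figures right for the term they are said to describe, and the plan nowhere presents the 2.6 divisor as a deliberate conservative choice.

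Two further replies also stand in part. The factor 0.2 is the pure random-intercept case, and a model called random coefficients would ordinarily allow random slopes; step 4 shows that this reduces the overstatement without removing it. And the clinic design effect would have the right form if its ρ were the ICC of patient slopes. A reader might infer that the clinic ICC is certainly one for levels, but the text does not say which it is. The fair criticism is that it is unspecified.

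**Conclusion.** The point holds. The printed minimum detectable values rest on the wrong patient-level factor (2.6 in place of 0.2 under exchangeable correlation) and on a one-arm comparison with a fixed UC slope.

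Under random intercepts, two equal arms and the plan's own clinic design effect, they are about 2.5 times too large. With patient slope SD 0.3 to 0.1 and visits at 0, 1 and 2 years, the ratio is about 1.8 to 2.4. These figures depend on the assumptions listed.

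Three stronger readings are not supported:

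- **A 13-fold variance error or 3.6-fold MDE error overall.** Those ratios cover one variance component, in one arm, with no random slopes.
- **The printed values are safely conservative.** A modest between-clinic slope SD, on which the documents are silent, removes or reverses the overstatement, so the net direction is unknown.
- **The trial is underpowered or the H1 test is invalid.** Nothing here shows either; the error lies in the power paragraph, not in the test of the interaction.

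**What to change.** Rewrite section 2.2.6.1:

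- Give the minimum detectable difference for treatment by years elapsed in outcome units per year, from the two-arm mixed model.
- State the residual variance, patient-slope variance, clinic-slope variance (or slope ICC), visit timing, and clinics and patients in each arm. Take these from pilot EHR data, or show a range.
- Say whether the clinic ICC refers to levels or slopes, and make the random effects in the Aim 1 Analytic Approach explicit.
- Make the patient range and the printed values agree: 4125 patients give 0.046 and 0.0625, not 0.044 and 0.061.
- State that a null H1 will be read mainly from the confidence interval for the interaction.

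The cost is one rewritten paragraph, a clarifying sentence on the model and a short calculation. No design change is needed.
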